9.5 PET Exams

PET exams of [¹⁸F]Flutemetamol and [¹⁸F]FDG will be acquired in each participant. Two PET/CT scanning sessions will be required. This is due to fact that both [¹⁸F]Flutemetamol and FDG are labeled with F-18 that has a 110-minute half-life, which does not allow for same day imaging. The FDG and [¹⁸F]Flutemetamol study procedures will be obtained on separate days usually within 10-14 days of each other. Typically these will be obtained over two separate days (consecutive if possible). However, this may not be possible due to scheduling issues, weekends, and other variables. The days of imaging will be scheduled according to scanner and cyclotron availability, and all days of imaging will be obtained within six weeks of each other. The exact order and timing of the two PET imaging sessions will vary according to logistics, scheduling, and tracer availability. Patients who are not postmenopausal for a minimum of one year or surgically sterile must have a serum pregnancy test performed within 48 hours prior to each research PET imaging. The procedures for each PET scan are similar as described below.

9.5.1 Day of Research PET Scan(s)

The patient will have the appropriate IV access placed for radiotracer administration. Access for temporal blood sampling, necessary for obtaining the input function for PET kinetic modeling, will be obtained using the heated-hand methodology for obtaining arterialized venous blood (FDG). The patient will be positioned comfortably on the PET imaging table. After positioning the patient in the gantry of the GE Discovery 710 PET/CT system, a topogram of the head will be obtained to confirm the correct positioning and identify the anatomic range for a single PET bed position covering the entire brain. A helical CT scan is then performed over the same anatomic range corresponding to the PET scan in order to perform attenuation correction. Thereafter the PET scans will then be acquired for either the dynamic FDG PET study or the static [¹⁸F]Flutemetamol PET study.

9.5.2 PET Tracer Administration Overview

Table 4. PET Tracer Administration: Route, Dosing, and Blood Sampling

Tracer	Route	Manner	Injected Dose	Scan Mode	Blood Sampling
¹⁸ F-FDG	IV	~60s push	~10.0 mCi	Dynamic	Heated-hand
[¹⁸ F]Flutemetamol	IV	~30s push	~5.0 mCi	Static	N/A

Each radiopharmaceutical will be prepared by the investigational drug radiochemists in the PET cyclotron facility at HCI on the day of the scanning session. It will be administered to the patient by a physician, nuclear medicine technologist, or trained nurse in the research PET imaging suite. The dynamic imaging procedure will take 70 minutes to complete for FDG.

No adverse events have ever been reported with the use or administration of FDG so reporting is not required.

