1.2 Primary Objective of Study - Synopsis

The exploratory objective of this study is to determine the association of amyloid plaque burden determined with [¹⁸F]Flutemetamol PET imaging, brain metabolism determined with FDG, and the anatomical and functional information obtained with fMRI and correlate these variables in 12 breast cancer patients experiencing CICI. We expect that up to 15 participants may be enrolled in this study. This will assure 12 evaluable patients (patients who have complete imaging results and blood data available for data analysis). In certain patients the blood data is not acceptable for final analysis because of difficulty in drawing it rapidly enough due to the vein collapsing during the rapid sampling required.

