8.4 Exclusion Criteria

- Patients with known allergic or hypersensitivity reactions to previously administered radiopharmaceuticals. Patients with significant drug or other allergies or autoimmune diseases may be enrolled at the Investigator's discretion.
- Adult patients who require monitored anesthesia for PET scanning.
- Patients who are too claustrophobic to undergo MRI or PET imaging.

- History of neurological disease known to affect cognition prior to initiating chemotherapy (e.g., stroke, head injury with loss of consciousness of >30 minutes, seizure disorder, demyelinating disorder, mental retardation, primary brain tumor, brain metastases, etc.)
- Current or past major psychiatric illness (e.g., schizophrenia, bipolar affective disorder)
- Evidence of stroke or mass lesion on CT or MRI scan
- History of alcoholism or other substance abuse
- Current use of cholinesterase inhibitors, other cognitive enhancers, antipsychotics, antidepressants, or anticonvulsant medications
- Current use of gabapentin or venlafaxine for hot flashes
- History of radiation therapy to the brain
- Uncontrolled diabetes or blood glucose >175 mg/dl on the day of the FDG-PET scan
- Currently pregnant
- Color blindness (cannot complete D-KEFS Stroop test)
- Moderate or Severe Depression as measured on the Beck Depression Inventory (BDI) – Short Form. The cut-off score for the BDI will be 8/9.

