11. REGULATORY AND REPORTING REQUIREMENTS

This study involves exposure to radiation and is appropriate for Human Use Subcommittee Review. FDG-PET is a clinically approved procedure for patients with cancer. However, for this research study, FDG is being performed under IND# 113,858 and [¹⁸F]Flutemetamol is being performed under IND#109,760 ([name] is IND holder for both INDs), as such the following FDA reporting of unexpected fatal or life threatening events, serious adverse events, and serious and unexpected adverse events will occur: (1) reporting any unexpected fatal or life threatening adverse experience associated with the use of [¹⁸F]Flutemetamol by telephone or fax no later than 7 calendar days after initial receipt of the information. (2) Reporting any adverse experience associated with the use of [¹⁸F]Flutemetamol, that is both serious (SAE) and unexpected in writing

no later than 15 calendar days after initial receipt of the information. (3) Submitting annual reports. The reportable events will also be submitted to the IRB using the University of Utah ERICA online system:

<https://erica.research.utah.edu/erica/Rooms/DisplayPages/LayoutInitial?Container=com.webridge.entity.Entity%5B0ID%5B5FD2DA60262617429607E459C0E09D92%5D%5D>

The descriptions and grading scales found in the revised NCI Common Terminology Criteria for Adverse Events (CTCAE) version 4.03 will be utilized for adverse event reporting (<http://ctep.cancer.gov/reporting/index.html>).

All appropriate research areas will have access to a copy of the CTCAE version 4.03 with modifications. A list of adverse events that have occurred or might occur (Reported Adverse Events and Potential Risks) can be found in Section 6 (Imaging Studies Information).

The reportable events will also be submitted to the IRB using the University of Utah ERICA online system:

<https://erica.research.utah.edu/erica/Rooms/DisplayPages/LayoutInitial?Container=com.webridge.entity.Entity%5B0ID%5B5FD2DA60262617429607E459C0E09D92%5D%5D>

Adverse events will be assessed for [¹⁸F]Flutemetamol immediately following the imaging scan. Additionally, a follow-up telephone call will be made to each participant within 1 day following their imaging scan. If the participant cannot be contacted at 1 day post-scanning, then we will continue trying to contact them for up to 7 days post-scanning.

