12.3 Reported Adverse Events and Potential Risks

Blood sampling entails the risks of minor discomfort, infection, bruising and bleeding. Radiation risk accompanies the use of radioisotopes in PET imaging. FDG-PET imaging is considered to be generally safe and effective. It has been approved by the Centers for Medicare and Medicaid for several clinical indications, using procedures identical to those used in this study. FDG is administered in trace doses and adverse effects have not been reported during its more than 20 years of use. Nevertheless the possibility exists for a rare allergic reaction.

The current use of [¹⁸F]Flutemetamol is investigational although it did receive FDA approval in October 2013. To date, it has been given to numerous individuals world-wide at the doses proposed here without significant adverse effect.¹²² Subjects scanned with PET are exposed to radiation. The amount of radiation exposure will be well within limits permitted to radiation workers by federal regulations. There is no known minimum level of radiation exposure that is recognized as being totally free of the risk of causing genetic defects (cellular abnormalities) or cancer. However the risk associated with the amount of radiation exposure that the subject will receive from this study is considered to be low.

Radioisotope injection requires the use of an intravenous catheter. There is a minimal risk of infection and bruising associated with the venipuncture required for the indwelling catheter. There can be discomfort from the requirement from lying quietly during imaging. Research data includes personal health information that can be inadvertently revealed to others. All of these risks are similar to those encountered during usual clinical care.

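### FDG injections have no scheduled adverse-event ascertainment and no explicit expedited route to the FDA, and the FDG waiver in 9.5.2 contradicts 11.1

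*Combined protocol and SAP*

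**What the plan says.** All references are to the combined protocol and SAP.

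- **The waiver.** Section 9.5.2, directly after the tracer table, states: "No adverse events have ever been reported with the use or administration of FDG so reporting is not required".
- **Regulatory status.** Section 11 states that "FDG is being performed under IND# 113,858 and [¹⁸F]Flutemetamol is being performed under IND#109,760", and gives this as the reason for the FDA reporting list that follows. Items (1) and (2) of the list (the 7-day and 15-day reports) are worded for flutemetamol alone. Item (3), annual reports, names no tracer.
- **Scheduled ascertainment.** Section 11: "Adverse events will be assessed for [¹⁸F]Flutemetamol immediately following the imaging scan". The follow-up call in section 11 names no tracer, but Appendix D attaches both the questionnaire and the next-day call to the flutemetamol scan. The Appendix E form is titled for flutemetamol.
- **Reporting window.** Sections 11.1 and 11.2 each limit required adverse-event reporting to the 24 hours after the flutemetamol injection.
- **Ordinary reporting.** The first sentence of 11.1 exempts events unrelated to flutemetamol from expedited reporting but still sends them to the IRB in the usual way.
- **Provisions that do not depend on the tracer.** The note under Table 5 in 11.2 covers grade 3 to 5 events leading to or prolonging hospitalization, whatever their attribution. Section 11.3 covers all deaths, and sends fatal and life-threatening events to the IRB within 24 hours. Section 11.4 has the DSMC review every SAE.

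**The concern.** The waiver rests on the absence of past reports, which is a weak reason for not looking in a study that gives the tracer under an IND. Section 12.4.2 itself describes FDG as investigational here.

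The FDG session is also the more demanding of the two. It is the only one with dynamic imaging (70 minutes) and heated-hand blood sampling (sections 9.5.1 and 9.5.2). Section 1.2 expects some veins to collapse during the rapid sampling, and 12.3 lists infection, bruising and bleeding among the sampling risks. Yet this is the session with no scheduled adverse-event follow-up.

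Two things are at stake: participant safety, and the completeness of what can be reported under the FDG IND. If events after FDG are not sought, an empty FDG safety record cannot be told apart from a record of no events.

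**Working it through.** The plan gives no figure on this point, so there is none to reproduce. The check is a count, followed by a comparison of the provisions.

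**1. Injections affected.** Inputs: one scan with each tracer per participant (section 9.5: "PET exams of [¹⁸F]Flutemetamol and [¹⁸F]FDG will be acquired in each participant"), and maximum enrolment (section 1.2: "We expect that up to 15 participants may be enrolled in this study").

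- Total injections = participants × 2 = 15 × 2 = 30.
- FDG injections = 15 × 1 = 15, so 15/30 = 50%.
- Among the 12 evaluable patients: 12 of 24, again 50%.

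This counts injections without a scheduled assessment. It does not count lost events.

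**2. What applies after each tracer.**

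| Provision | Flutemetamol | FDG |
|---|---|---|
| Assessment right after the scan (11, App. D, E) | yes | not specified |
| Next-day call (11, App. D) | yes | not specified in App. D |
| 24-hour reporting window (11.1, 11.2) | yes | no |
| FDA 7-day and 15-day items (11; 7-day item repeated in 11.2, 11.3) | yes | not named |
| Ordinary IRB reporting (11.1, first sentence) | not the route described | yes, but waived by 9.5.2 |
| Grade 3–5 hospitalization (11.2 note) | yes | yes |
| Deaths; fatal or life-threatening events to the IRB (11.3) | yes | yes |
| DSMC review of SAEs (11.4) | yes | yes |

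Table 5 does not label its columns by tracer and does direct some reports to the FDA. However, 11.1 exempts non-flutemetamol events from expedited reporting, and the sentence just before the table restricts reporting to the period after flutemetamol. A reader therefore cannot take Table 5 as an explicit FDG route.

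**3. The rules applied to three events after FDG.**

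- *Non-serious rash.* Section 9.5.2: no report. The 24-hour sentence in 11.1: not required. The first sentence of 11.1: report to the IRB. These cannot all be followed.
- *Bruising from the blood sampling.* The wording of 9.5.2 concerns FDG itself and does not clearly reach this. The 24-hour sentence says not required, while the first sentence of 11.1 says report to the IRB. The conflict remains, now inside 11.1.
- *Life-threatening reaction.* Section 11.3 sends it to the IRB within 24 hours and 11.4 to the DSMC. The 7-day FDA clause names flutemetamol only.

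**4. Overlap by scheduling.** Section 9.5 prefers consecutive scan days but allows up to six weeks. If flutemetamol comes first and FDG follows the next day, an early FDG event could fall inside the flutemetamol window or be mentioned on the flutemetamol call. That depends on scan order and spacing, which the protocol leaves to logistics.

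**The case against.** The strongest reply is that directing active follow-up at flutemetamol is a deliberate choice. The protocol describes FDG as FDA approved (study summary), without known toxic effects (section 5.1) and clinically approved for cancer patients (section 11). Serious outcomes are caught whichever tracer was given. Whether the FDG IND demands more depends on its terms, which are not in the documents. Most of this stands. It explains a lighter schedule after FDG, but it does not resolve the opposing instructions in 9.5.2 and 11.1, or explain why two INDs introduce a list whose event items serve one.

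A reader might also infer three stronger points that the documents do not support:

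- *That half the injections have no safety capture.* Sections 11.2 to 11.4 cover qualifying hospitalizations, deaths, life-threatening events and SAEs after either tracer, and the first sentence of 11.1 covers the rest.
- *That an FDG reaction or a sampling complication would certainly not be collected.* The text conflicts, so collection is uncertain; it is not ruled out. For sampling complications, 9.5.2 is not clearly a waiver at all.
- *That 12.3 and 8.4 contradict the waiver.* Section 12.3 agrees that no FDG effects have been reported before adding "Nevertheless the possibility exists for a rare allergic reaction"; disclosing a possible risk does not contradict a reporting rule. The exclusion of "Patients with known allergic or hypersensitivity reactions to previously administered radiopharmaceuticals" is an entry safeguard and says nothing about reporting. Both show that the risk was recognised, and no more.

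**Conclusion.** The point holds for scheduled ascertainment and for the reporting path. One of the two injections per participant (15 of 30 at full enrolment) has no scheduled adverse-event assessment, and FDG-associated events have no explicit expedited path to the FDA. The waiver in 9.5.2 and the flutemetamol-only 24-hour sentence contradict the opening of 11.1, so non-serious FDG reactions may go unrecorded by staff who are following the protocol. Serious outcomes remain covered, although that cover relies on someone learning of the event.

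The conclusion assumes one injection of each tracer per participant and reads the next-day call as Appendix D does. The documents give no FDG event rate for this setting, so the number of events that might be missed cannot be estimated. Sample size and the primary analysis are unaffected. The change is worth making because the contradiction is plain and the remedy cheap.

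**What to change.** - Delete the waiver sentence from 9.5.2 and reconcile that section with 11.1, so that there is one rule for events after FDG.
- Extend the reporting clauses in 11, 11.1, 11.2 and 11.3, including the 24-hour window, to either study tracer. Reword the first sentence of 11.1 so that ordinary IRB reporting applies to events associated with neither tracer.
- Use the Appendix E questionnaire and the next-day call after both PET sessions, and amend the Appendix D schedule and the form's title to match. Add a line to the form for blood-sampling complications: it has items for injection-site reaction, pain and fever, but none for bruising, bleeding or infection.

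The cost is at most one extra short form and one extra call per participant, so 15 of each at full enrolment. Any participants scanned before the change should be described as not having been actively followed after FDG, so that missing records are not read as no events.

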9.6 Tissue Collection and Analysis

All patients enrolled on this study may have recent surgical pathology or biopsy information available and tissue specimen reports and assessments will be analyzed by the study PI and co-investigators.

10. METHODS FOR EVALUATION OF IMAGING STUDIES/ DATA ANALYSIS AND STATISTICS

Each PET imaging study will be evaluated using qualitative, semi-quantitative, and fully-quantitative analysis techniques that have previously been evaluated by us and other groups^{116,139,140} and represent the standard and accepted means of evaluating static- and dynamic-PET images for these tracers. These assessments are described below for each tracer.

[figure not shown]
10.1 ¹⁸F-FDG-PET Imaging

10.1.1 FDG Semi-Quantitative Assessment

FDG-PET data will be analyzed using CortexID Suite, a software application provided by GE Healthcare. The software has a large group of normal healthy controls of varying ages included as the normal database so the provided Z scores are in comparison to age and sex matched controls. Cortex ID Suite is an FDA approved brain image analysis software designed to quantify FDG uptake measured with PET and PET-CT brain scans. The software aids clinicians in the assessment of FDG-PET scans by providing automated analysis through quantification of the comparison of local peak FDG uptake activity values, at standardized bilateral anatomical locations, compared with the corresponding reference normal peak activity in age- stratified normal control subjects. The resulting quantification is presented through 3D Stereotactic Surface Projection (SSP) maps of the brain as initially described by Minoshima et al.¹⁴¹ CortexID allows for user generated information on the relative changes in metabolic activity normalized to the pons presented as regional and global Z-scores between a subject's images and age-stratified controls. The regions of interest that will be assessed include: parietal association, temporal association, frontal association, occipital association, posterior cingulate, anterior cingulate, medial frontal, medial parietal, visual, cerebellum, pons, average association, averaged cerebral, global average.

10.1.2 FDG Fully-Quantitative Assessment

Compartment modeling techniques will be applied to the dynamic PET data to obtain estimates of kinetic rate parameters (K_1 , k_2 - k_4) and FDG net uptake (K_{net}). Individual rate parameters will be computed using full compartment-modeling techniques according to the two-tissue compartment model shown below. The commercially available PET analysis software (e.g. PMOD Technologies LTD., Zurich, Switzerland) will be used. The net uptake parameter will be computed from both full compartment modeling and Patlak graphical analysis^{139,140} both of which are standard and accepted methods.

A region-of-interest (ROI) will be drawn over the defined cortical brain region on the summed static FDG PET image. The summed image will be co-registered and fused to the patient's MRI. This will allow for regional determination of brain glucose metabolic rates. For each ROI the metabolic rate obtained can then be correlated with available clinical data, neuropsychological data, and the regional amyloid plaque burden SUV.

10.2 [¹⁸F]Flutemetamol-PET Imaging

The primary assessment of amyloid plaque burden will be with visual assessment of abnormal cortical flutemetamol uptake as outlined in the recently approved Vizamyl (flutemetamol F 18 injection) prescribing information (section 2.5).¹ This will be a binary assessment of the images being positive or negative for increased and abnormal flutemetamol uptake and thus increased amyloid plaque burden. A secondary analysis of flutemetamol binding will occur using a regional semi-quantitative technique as described by Vanderberghe et al.¹²³ In this technique, a semi-quantitative global composite of standardized uptake value ratios (SUVRs) in the cerebral cortex which is obtained and normalized to the cerebellum or pons. The following regions are averaged to yield the global composite: lateral frontal, lateral temporal, lateral parietal, anterior cingulate, and posterior cingulate. This will yield a global composite for [¹⁸F]Flutemetamol-PET data. GE proprietary software (CortexID Suite) is available in our laboratory and will be used to determine both regional SUV values and a composite SUVR for [¹⁸F]Flutemetamol uptake. This database also contains [¹⁸F]Flutemetamol scan data from 105 healthy volunteers and has been validated to be over 99% concordant with visual reads using 172 scans from AD, MCI, and healthy controls using a threshold Z score of 2 (which corresponds to a composite SUVR of 0.59). This software will provide the control population to which we will compare our symptomatic CICI patients. Z scores obtained for the study patients using this software will then be correlated with available clinical data, neuropsychological data, and the regional FDG Z scores or metabolic rates.

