10.3 Magnetic Resonance Imaging

Participants will be imaged using a Siemens Trio 3T MRI scanner with 32 channel head coil using a magnetization prepared rapid gradient echo (MPRAGE) acquisition with isotropic image resolution of 1.0 mm and full head field of view. Imaging will be performed in the sagittal plane with repetition of sequences deemed at the time of acquisition to exhibit patient head motion or other artifacts. Images will be analyzed using SPM12 toolbox for MATLAB, with linear normalization to Montreal Neurological Institute (MNI) template brain space, segmentation of gray matter, white matter, CSF, and volumetric quantitation of gray matter voxels and gray matter density compared to previously acquired control cohorts using the same sequence, with age-matched normative database. Regions of abnormal volume and density will be identified in 116 regions of the automated anatomical labeling (AAL) brain atlas.

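### The kinetic FDG regions are drawn on the FDG image being measured, and nothing ensures that they match the CortexID regions supplying the paired amyloid values

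*Combined protocol and SAP*

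**What the plan says.** Section 10.1.2 describes the region step of the kinetic FDG analysis in three moves. First, the outline: "A region-of-interest (ROI) will be drawn over the defined cortical brain region on the summed static FDG PET image". Second, the MRI: "The summed image will be co-registered and fused to the patient's MRI". Third, the use of the result: "For each ROI the metabolic rate obtained can then be correlated with available clinical data, neuropsychological data, and the regional amyloid plaque burden SUV".

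The amyloid side is in section 10.2: "GE proprietary software (CortexID Suite) is available in our laboratory and will be used to determine both regional SUV values and a composite SUVR". The composite is built from five named areas: "The following regions are averaged to yield the global composite: lateral frontal, lateral temporal, lateral parietal, anterior cingulate, and posterior cingulate". The same section states the pairing from the amyloid side, with Z scores to be "correlated with available clinical data, neuropsychological data, and the regional FDG Z scores or metabolic rates".

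There is a second FDG measure. Section 10.1.1 says "FDG-PET data will be analyzed using CortexID Suite, a software application provided by GE Healthcare", and that software samples uptake at standardized anatomical locations. Section 10.4 names the CortexID Z scores as the FDG imaging parameter and does not list the kinetic rates.

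An anatomical atlas appears only for the structural MRI, in section 10.3: "Regions of abnormal volume and density will be identified in 116 regions of the automated anatomical labeling (AAL) brain atlas".

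**The concern.** When a region is outlined on the image that is then measured, the signal can help set the region's edge. Cortex with reduced FDG uptake can look like white matter or background, and a person drawing on the uptake image may leave it out. The region then loses tissue where metabolism is lowest, and a focal deficit reads smaller than it is. That would be a differential error: it would be largest in the patients with the most focal loss, which is what exploratory endpoint III (sections 7.4 and 10.4) looks for.

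The second issue is the pairing. If the metabolic rate comes from a drawn region and the amyloid value from a CortexID region, differences between the two outlines can weaken the regional FDG–amyloid correlation. That association is part of the stated objective (section 1.2). Section 2.5 also presents dynamic quantitative FDG as what this study adds to the earlier, non-quantitative FDG study in women treated with chemotherapy, and this region step produces those rates.

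**Working it through.** **1. The plan's own design figure.** Section 10.5 gives n = 12, rejection at 4 or more positives, a null rate of 12%, an alternative of 42%, one-sided 0.05 and 80% power. Exact binomial: P(X ≥ 4 | 12, 0.12) = 0.046 and P(X ≥ 4 | 12, 0.42) = 0.815. The figure reproduces. The test uses flutemetamol only, so nothing below changes it.

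**2. What the text settles and what it leaves open for the kinetic analysis.**

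| Question | Text |
|---|---|
| Image on which the region is drawn | Summed FDG image (10.1.2) |
| MRI named as source of the outline | No; fusion is mentioned after drawing (10.1.2) |
| Region list, edge rule, or blinding of the person drawing | None given |
| Source of the paired amyloid value | CortexID (10.2) |
| Flutemetamol registered to the MRI or to FDG | Not described |
| One mask applied to both tracers | Not described |

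**3. How much a focal deficit could shrink (all inputs assumed).** Let a fraction f of a region's voxels be reduced by d, and let a fraction t of those voxels fall outside the outline.

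- True deficit = f·d.
- Deficit read = f(1 − t)d / (1 − f·t).

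With f = 0.20 and d = 0.30, the true deficit is 6.0%.

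- t = 0.25: 0.045/0.95 = 4.7%
- t = 0.50: 0.030/0.90 = 3.3%
- t = 0.75: 0.015/0.85 = 1.8%
- t = 1: 0%

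With f from 0.10 to 0.40 and d from 0.20 to 0.30, the true deficit runs from 2% to 12%. With half the affected voxels left out, it reads 1.1% to 7.5%.

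**4. Dependence on the edge rule and the shape of the deficit (all inputs assumed).** Take voxel values as normal with mean 1 and SD 0.15. Compare each region with a normal region under the same rule.

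| True deficit | Lowest 10 / 20 / 30% dropped | Only voxels above 0.75 to 0.85 kept |
|---|---|---|
| 4%, focal (20% of voxels down 0.20) | 3.4 / 3.0 / 2.7% | 1.8 to 0.9% |
| 6%, focal (20% of voxels down 0.30) | 4.7 / 3.9 / 3.3% | 1.4 to 0.5% |
| 6%, uniform | 5.8 / 5.7 / 5.6% | 4.5 to 3.3% |

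For the uniform deficit under the percentile rule, the normal region's mean after dropping the lowest p is 1 + 0.15·φ(z)/(1 − p), where z is the standard normal p-quantile. That is 1.029, 1.053 and 1.075, and 0.06 divided by these gives 5.8%, 5.7% and 5.6%.

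**5. Dilution of the correlations (inputs assumed).** If outline placement adds noise of 3% to 5% to a between-patient SD of 10%, a true correlation is multiplied by 1/√(1 + (noise/SD)²), which is 0.96 to 0.89.

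For context at n = 12, by Fisher's z, 80% power at two-sided 0.05 needs r = tanh((1.960 + 0.842)/√9) = 0.73. Multiplying 0.73 by 0.9 gives 0.66, with about 66% power; multiplying by 0.8 gives 0.58, with about 52%. The plan treats these correlations descriptively and claims no power for them.

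**The case against.** The strongest reply is that section 10.1.2 speaks of a cortical region already defined, mentions no uptake contour or threshold, and fuses the image to the MRI to allow regional determination. On that reading, anatomy guides the outline and the summed image is only where it is placed. The text permits this reading but does not state it. If it is what is meant, saying so settles most of the first issue.

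Second, the CortexID FDG Z scores use standardized locations with no drawn region, are the FDG parameter named in section 10.4, and can serve endpoint III. This stands and limits the scope: a reader might infer that endpoint III as a whole is biased toward no effect, and the documents do not support that.

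Third, a reader might infer that the two tracers are measured in different tissue. That is not shown. The text shows only that identical regions are not ensured; regions of the same name may overlap heavily. The CortexID-to-CortexID pairing also keeps both tracers in one software suite, although the region lists there are not identical either (parietal association for FDG, lateral parietal for amyloid).

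Fourth, the sizes are assumed. The largest shrinkage needs a fixed uptake threshold, which the plan never mentions, and a focal deficit. A uniform 6% loss barely moves under the percentile rule. This stands in full.

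**Conclusion.** The point holds for the exploratory correlations that use kinetic metabolic rates. As written, the outline is made on the image being measured, the MRI is not named as its source, and no step gives the two tracers the same regions. Low-uptake cortex may be left out, and the paired values may not cover the same tissue.

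The direction of the risk is toward understating a focal deficit and weakening the regional FDG–amyloid correlation. Its size cannot be taken from the documents. The illustrations run from almost nothing (uniform loss, percentile rule) to most of the deficit (focal loss, fixed threshold), and every input is an assumption.

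The CortexID FDG Z-score analyses, the primary amyloid test, the 12 evaluable patients and the stated power are unaffected. The change is worth making because it is cheap and removes an analyst choice that can depend on the outcome.

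**What to change.** In section 10.1.2, replace the sentence on drawing the region with wording such as: Regions will be defined on each patient's MPRAGE (for example, the AAL labels of section 10.3, brought to native space and restricted to segmented grey matter) without reference to FDG uptake. Both the FDG and the flutemetamol images will be co-registered to the MRI, and the same masks will be applied to the dynamic FDG and the flutemetamol images for the correlations in this section. No region will be drawn or edited on the FDG uptake image.

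Keep the CortexID outputs for the Z-score analyses, and say in section 10.2 which amyloid values are paired with which FDG values.

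Cost: protocol wording and some image processing, with no new scans or patients. The MPRAGE, the grey-matter segmentation, the atlas labelling and the FDG–MRI co-registration are already planned. The flutemetamol–MRI registration and the transfer of masks to native space are additional, since section 10.3 describes atlas regions only after linear normalization to template space. Registration error will then affect the region edges, but those edges will no longer be set by the FDG signal.
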